15.1 Statistical considerations

The proportion of patients that did not require mechanical ventilation or die within 29 days of randomization will be recorded as a preliminary assessment of the efficacy of duvelisib in this setting.

Definition of subjects evaluable for efficacy response

Subjects who completed screening and enrollment procedure and who are randomized to receive duvelisib/placebo will be evaluable for efficacy endpoints on an intent-to-treat basis.

Definition of NIAID scale

The clinical response to study drug is defined as the first day on which the subject satisfies the criteria of a score of 5 or greater in the following categories from the NIAID ordinal scale. The NIAID ordinal scale is an assessment of the clinical status at the first assessment on a given study day. The scale is as follows: 1) Death; 2) Hospitalized, on invasive mechanical ventilation or extracorporeal membrane oxygenation (ECMO); 3) Hospitalized, on non-invasive ventilation or high flow oxygen devices; 4) Hospitalized, requiring supplemental oxygen; 5) Hospitalized, not requiring supplemental oxygen - requiring ongoing medical care (COVID-19 related or otherwise); 6) Hospitalized, not requiring supplemental oxygen - no longer requires ongoing medical care; 7) Not hospitalized, limitation on activities and/or requiring home oxygen; 8) Not hospitalized, no limitations on activities.

Definition of the primary efficacy endpoint

The proportion of patients who do not require mechanical ventilation (e.g. intubation, high-flow O₂ Bi-PAP or AIRVO) and who survive to 4 weeks after randomization will be used as the primary measure of efficacy.

Study design

This is a randomized placebo-controlled double blind/double masked phase 2 study to explore the efficacy of exposure to a PI3K inhibitor in patients with severe COVID-19. Subjects who are randomized to receive duvelisib or placebo will be evaluable for the primary and secondary efficacy analyses. All subjects with any exposure to duvelisib will be evaluable for toxicity (please see section 13.3 on grading of toxicities). A total of 80 subjects will be planned for analysis of the primary and secondary endpoints. We estimate that five subjects will be enrolled every month. One interim analysis is planned upon 50% (n=40) of subjects enrolled, which allows us the

Protocol Title: Duvelisib Ameliorates Manifestations of Pneumonia in Established Novel Coronavirus Infection (DAMPEN-CI)

opportunity to stop the trial early due to futility or safety concerns. The only groups that will have access to unblinded interim data: (a) an independent data monitoring committee (IDMC); and (b) an independent statistical team whose role will be to generate the reports to be reviewed by the IDMC. The responsibility of any data-informed recommendations regarding continuing/stopping the study or modifying the study design/protocol be restricted to the IDMC.

Power Calculation

The reported incidence of death or mechanical intubation for patients with severe COVID-19 is approximately 40% (1). Local experience with COVID-19 patients at the Emory hospitals is consistent with this estimate, as 29% of all SARS-CoV-2 positive patients (n=800) are admitted to the ICU with COVID-19, and that 22% of all admitted patients are intubated, and 37% of intubated patients die in hospital. A favorable and clinically significant result from treatment with duvelisib in high-risk COVID-19 patients would be to reduce the composite incidence of death/mechanical ventilation from 40% to 15%. A sample size of 40 subjects for each treatment group will have >80% power to detect a 25% absolute reduction in the proportion of subjects who experience death or mechanical ventilation, comparing a predicted proportion of 40% death or intubation in the control arm to 15% death or intubation in the experimental arm receiving duvelisib treatment. The calculation is based on 10% type 1 error rate and two-sided Mantel-Haenszel test with one planned interim analysis when approximately 50% of sample enrolled (N=20/treatment). For

Analysis of Primary Endpoints

Analysis of the primary end-point will be based upon an intent-to-treat analysis of all subjects who are randomized to receive duvelisib/placebo. The primary endpoint is the proportion of patients who will require mechanical ventilation or experiencing death within 4-weeks (29 days) after randomization, which will be estimated with the corresponding 95% Clopper-Pearson confidence interval for the two arms separately. Fisher's Exact test will be used to test the difference between the two arms. In addition, a logistic regression will be used to estimate the odd ratio between the two arms controlling for the baseline covariates for an improved precision of the estimation (30).

Analysis of Secondary Endpoints

Evaluable subjects will be all subjects who were randomized to receive duvelisib or placebo. The definition of secondary endpoints are listed in section 2. The descriptive statistics will mainly be applied to all secondary endpoints by treatment arms separately, such as frequency and percentage for categorical endpoints and mean, median, and standard deviation for numerical endpoints. They will be compared between treatment arms by Fisher's Exact test for categorical endpoints and Wilcoxon Rank-Sum test for numerical endpoints. For biomarkers measured repeated over time, generalized estimating equation (GEE) model will be used to test the difference in change pattern over time by two treatment groups using a nonlinear model. P-value will be adjusted for multiple comparison if necessary. Time to recovery is as the days from randomization to reach the desired NIAID ordinal scale ≥ 5 , a log-rank test will be used to compare the difference between the two arms. Survival rate at day 50 - 60 will be estimated by Kaplan-Meier method with log-rank test.

Interim Analysis for futility

The responsibility of any data-informed recommendations regarding continuing/stopping the study or modifying the study design/protocol be restricted to the independent data monitoring committee (IDMC), which is a part of the Winship data safety monitoring committee (DSMC). Upon 20 enrolled for each arm, an interim analysis will be carried out by two-sided Mantel-Haenszel test. O'Brien-Fleming boundary for futility is 2.373 on the Z score (equivalently: 0.991 on the fixed sample p-value scale). The trial may be terminated due to futility, or

Protocol Title: Duvelisib Ameliorates Manifestations of Pneumonia in Established Novel Coronavirus Infection (DAMPEN-CI)

following review by the IDMC of clinical and laboratory immune-monitoring data. Otherwise, the trial will continue enrolling patients until all 80 patients enrolled.

Stopping Rule for Safety

At the interim analysis (20 patients/arm), the incidence of death or mechanical ventilation, grade ≥ 3 elevations in liver transaminases, or neutropenia will be estimated. We assume that the underline rate is 40%, 10%, or 24% for the three incidences in placebo group respectively, and if the rate in duvelisib group is $\geq 15\%$ higher than that in the placebo group in either of the three incidences, the trial may be stopped due to the safety concern. It also translates to stop the study if 3 or more excess events in duvelisib group are observed in either of the three incidences. Operating Characteristics, the probability of trial stopping due to ≥ 3 excess events based one simulation study, is listed in the below table.

AEs	Underline event rate in Placebo arm	Underline event rate in Duvelisib arm						
		5%	10%	20%	30%	40%	50%	60%
death or mechanical ventilation	40%	0%	0.02%	0.7%	4.8%	16.6%	37.4%	62.7%
grade ≥ 3 elevations in liver transaminases	10%	0.79%	5.7%	32.8%	65.8%	87.9%	97.2%	99.7%
neutropenia	24%	0.07%	0.6%	7.3%	26.1%	52.7%	77.3%	92.6%

In addition to the study stopping rules based an interim analysis, the Independent Data Monitoring Committee (IDMC) will review, on a monthly basis, the number of Grade 3 and/or Grade 4 adverse events in each arm, including neutropenia and elevated transaminases, and consider stopping or suspending accrual to the study if the frequencies of Grade 3 or Grade 4 adverse events are significantly higher among subjects in the duvelisib arm compared with subjects in the control arm.

Analysis of Safety Data

The primary safety endpoints include death or mechanical ventilation, grade ≥ 3 elvation in liver transminases, and neutropenia within 4 weeks. The cumulative incidence rate of each safety endpoint will be calculated with 95% confidence interval by randomized arms, and compared by Fisher's exact test.

Handing of Missing Data

For the safety endpoints and secondary endpoints, missing data will not be imputed, summaries and analyses will be based on the observed cases. For the primary efficacy analysis, every effort will be made from the informed consent form design to clinical follow up to reduce the missing data. Patients withdraw consent before the primary endpoint can be measured will be replaced.

Demographics and Baseline Characteristics

Summary statistics and frequencies for the following characteristics will be described by randomized arms: ECOG, Race, Ethnicity, Age, Sex, Body mass index (BMI), Medical history of hypertension, diabetes, asthma, chronic obstructive pulmonary disease, History of and treatment for cancer, History of coronary artery disease (prior MI, CABG, coronary artery stent, or medical management), History of prior pulmonary infections (TB, pneumonia, influenza), Allergies

Subgroup analyses

None

15.2 Data/specimens:

Source Documents

Source data is all information, original records of clinical findings, observations, or other activities in a clinical trial necessary for the reconstruction and evaluation of the trial. Examples include medical records (hospital records, office charts), laboratory results, imaging scans and reports, EKGs, patient diaries, videos, photographs, pharmacy dispensing, and other records, investigator or patient completed questionnaires involved in the clinical trial.

Case Report Forms

The case report form (CRF) will be the primary data collection instrument for the study. All data requested on the CRF will be recorded and all entries will be recorded into an electronic data capture system by authorized personnel. The principal investigator is responsible for assuring that the data entered into the CRF are complete, accurate and that entries are updated in a timely fashion. Data will be entered in the clinical research data management system – REDCap - per Winship SOP 4.2 Data Completion Metrics. REDCap will be used to record all study related information and data for all registered subjects, including their assigned patient ID. All data submitted must be accompanied by supporting source documents, where applicable and as outlined in the protocol-specific monitoring plan. Data completion will be reviewed monthly. In situations where there are significant delays of data completion, the Associate Director of Clinical Research or the Director of Clinical Trials may temporarily suspend enrollment. All data must be entered in the timeframe required at each site, but no later than 30 days following registration and each visit completion. All queries are to be resolved within 4 weeks of issue. The coordinating center multi-site coordinator will provide REDCap training and request access to the appropriate staff at the participating site.

Procedures to Ensure Capturing Data for the Primary End-point

All patients who maintain consent to be followed for additional outcome information will remain in the study through the end of the double-blind period collection of safety and efficacy assessments. Subjects discharged from the hospital prior to the last protocol-specified assessment on day 29 will be followed as out-patients with in-person or telehealth visits. Survival status at day 50 - 60 will be captured in all subjects who have not withdrawn consent for follow-up by contacting the patient via a telehealth visit or other approaches (e.g., telephone calls, texts, and emails to the patient and close contacts). In the absence of direct or indirect contact with the subject, a vital records search will be performed to assess survival status of each subject.

Data Retention

All study documents will be retained for at least two years after the last approval of a marketing application in their country and until there are no pending or contemplated marketing applications in their country.

Transmission of Data:

Blood samples for T-cell phenotyping from secondary sites will be cryopreserved and shipped to Emory University in real-time. Patient samples will be cryopreserved by using Crystor Media (please see Appendix F). Emory University will cover the cost of shipment of blood samples. All patient samples for T-cell phenotyping will be analyzed at Emory University to ensure uniform analysis. Clinical data (ORR and rates of CRS, neurotoxicity, ICU

transfers) will be captured with chart review at Emory University and secondary sites. Data will be uploaded into RedCap. There will be monthly meetings (tele-conference) with each site's PI to review the study, enrollment and reporting of data.

Publication Plan

The results of the study should be available within 12 months of completion of the study. The end of the study is the time point at which the last data items are to be reported or after the outcome data are sufficiently mature for analysis. A full report of the outcomes will be made public no later than three years after the end of the study.

16. Provisions to Monitor the Data to Ensure the Safety of Participants

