To compare the incidence of mechanical ventilation or death in subjects with severe COVID-19 given placebo or oral duvelisib.	The primary end-point is a composite endpoint of mechanical ventilation or death within 4 weeks of randomization.
Secondary	
Secondary Objectives are to compare the duvelisib cohort to the placebo cohort with respect to:
 
1) Days to recovery as assessed by ACTT endpoints as the time to recovery (Day 1 through Day 29) to satisfy a score of ≥ 5 from the following eight categories from the NIAID ordinal scale. The scale is as follows: 1. Death; 2. Hospitalized, on invasive mechanical ventilation or extracorporeal membrane oxygenation (ECMO); 3. Hospitalized, on non-invasive ventilation or high flow oxygen devices; 4. Hospitalized, requiring supplemental oxygen; 5. Hospitalized, not requiring supplemental oxygen - requiring ongoing medical care (COVID-19 related or otherwise); 6. Hospitalized, not requiring supplemental oxygen - no longer requires ongoing medical care; 7. Not hospitalized, limitation on activities and/or requiring home oxygen; 8. Not hospitalized, no limitations on activities.2) Duration of hospitalization3) Death within 29 days of randomization4) ICU transfer within 29 days of randomization5) ECOG performance status at day 15 and 29 of randomization6) Incidence of grade III-V adverse events or SAEs (as defined by CTCAE version 5)7) Documented secondary bacterial or viral infection within 29 days of randomization.8) Mean frequencies of Th1 and Th17 T cells in blood mononuclear cells at 1, 2 and 4 weeks9) Mean levels of inflammatory serum biomarkers at 1, 2 and 4 weeks10) Gene expression profiles of T cells at 1, 2 and 4 weeks

OBJECTIVES	ENDPOINTS
11) Median titers of IgG antibodies to SARS-CoV-2 at 4 weeks 12) Survival at day 50-60 after randomization	

3. Background

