9.1 Inclusion Criteria

1. Hospitalized in participating facility.
2. Documentation of pneumonia with radiographic evidence of infiltrates by imaging (e.g., chest x-ray or CT scan).
3. Laboratory-confirmed SARS-CoV-2 infection as determined by PCR or other authorized or approved assay in any specimen collected within 72 hours prior to enrollment. Note – An exception must be requested to the Sponsor if ≥72 hours since positive test.
4. Symptoms suggestive of severe systemic illness with COVID-19, such as respiratory rate ≥ 30 breaths per minute, heart rate >125 beats per minute, oxygen saturation (O₂ sat) in the blood of <93% on room air at sea level or PaO₂/FiO₂ < 300 (see Appendix A).
5. 18 years of age or older
6. Patients with hematological parameters at screening consistent with ≤ grade 2 NCI CTCAE v5.0 toxicity: hemoglobin ≥8 g/dL, platelet count ≥50,000 K/mcl, an absolute neutrophil count (ANC) ≥1,000/mm³, and an absolute lymphocyte count (ALC) ≥500/mm³.

Protocol Title: Duvelisib Ameliorates Manifestations of Pneumonia in Established Novel Coronavirus Infection (DAMPEN-CI)

7. Patients with laboratory measurements of liver function at screening consistent with \leq grade 2 NCI CTCAE v5.0 toxicity: alanine aminotransferase (ALT) \leq 5X ULN; aspartate aminotransferase (AST) \leq 5X ULN; and bilirubin \leq 3X ULN.

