Validated definition for severe disease (<https://covid19treatmentguidelines.nih.gov/overview/management-ofcovid-19/>) is based on the following:

Confirmed SARS-CoV-2 infection (by PCR test) with fever or suspected respiratory infection, plus one of the following:

- a. respiratory rate > 30 breaths/min;
- b. severe respiratory distress; or
- c. SpO₂ ≤ 93% on room air at sea level or PaO₂/FiO₂< 300.

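### A hospitalized patient who qualifies on respiratory rate without oxygen scores 5 at entry and is counted as recovered on Day 1, which dilutes the time-to-recovery comparison

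*Combined protocol and SAP*

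**What the plan says.** Section 15.1 defines clinical response as "the first day on which the subject satisfies the criteria of a score of 5 or greater". It adds: "The NIAID ordinal scale is an assessment of the clinical status at the first assessment on a given study day". The boundary lies between "4) Hospitalized, requiring supplemental oxygen" and category 5, "Hospitalized, not requiring supplemental oxygen - requiring ongoing medical care (COVID-19 related or otherwise".

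The table in Section 2 sets the window: "the time to recovery (Day 1 through Day 29) to satisfy a score of ≥ 5". The synopsis lists the eight categories without a threshold. Under Analysis of Secondary Endpoints, Section 15.1 says "Time to recovery is as the days from randomization to reach the desired NIAID ordinal scale" of 5 or more, compares the arms by log-rank test, and takes every randomized subject as evaluable.

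Entry is set in Section 9.1. Patients must be in hospital. Criterion 4 gives an open list of alternatives: respiratory rate of at least 30, "heart rate >125 beats per minute", low room-air saturation, or PaO2/FiO2 below 300. It points to Appendix A, where one item is enough; "respiratory rate > 30 breaths/min" is on that list and heart rate is not. Neither text requires supplemental oxygen. The only exclusion based on respiratory support (Section 9.2) is at the high end: intubation, high-flow oxygen, Bi-PAP or AIRVO.

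**The concern.** The eligibility rule and the recovery rule overlap. A patient can be ill enough to enter and, on the same day, well enough to count as recovered. Nothing in Section 2 or Section 15.1 requires a starting score of 4 or less, an improvement from baseline, or a sustained score.

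Such patients become events on Day 1 in both arms, before study drug can act. In expectation they add nothing to the difference between arms, yet they add variance to the test and leave every later risk set. They also shorten the reported median time to recovery. Randomization is stratified by site only, so a chance imbalance in their number would put unequal counts of immediate recoveries in the two arms. Time to recovery is the first secondary endpoint listed in Section 2.

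**Working it through.** **Step 1: the logic.** The plan states no power, event count or recovery rate for this endpoint, so there is no figure to reproduce. Reading the rules in order:

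1. Hospitalized, with a respiratory rate above 30: meets the severity item in both criterion 4 and Appendix A.
2. Not on oxygen: not excluded by Section 9.2.
3. In hospital, no oxygen needed, care still needed: score 5.
4. Score 5 at the first Day 1 assessment: the threshold is met on the first day of the window.
5. All randomized subjects are analysed: the patient enters the log-rank test as a Day 1 event.

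**Step 2: what a Day 1 event does to the test.** The log-rank statistic is Z = Σ(O − E)/√ΣV, where at each event day V = d × p(1 − p) × (n − d)/(n − 1), with d events among n at risk and a share p in one arm. If 20% of 80 patients (16) start at 5 and p = 1/2, those 16 events alone give V = 16 × 0.25 × 64/79 = 3.24, with expected O − E of zero. Only 64 patients are left to carry information.

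**Step 3: size.** Inputs from the plan: 40 per arm, two-sided 10% (the level stated for the primary endpoint), follow-up to Day 29. Inputs assumed here: exponential recovery times rounded up to whole days, hazard ratio 1.6, control median 10 or 28 days, and a share f set to recover on Day 1. Daily hazards are ln 2/10 = 0.0693 (control) and 0.0693 × 1.6 = 0.111 (active), or ln 2/28 = 0.0248 and 0.0396. Simulated power, with simulation error of one to two points:

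| Share at score 5 (patients of 80) | Median 10 days | Median 28 days |
|---|---|---|
| 0 | 63% | 49% |
| 10% (8) | 58% | 40% |
| 20% (16) | 48% | 36% |
| 30% (24) | 42% | 29% |

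With a 10-day median and other hazard ratios, going from 0 to 30% takes power from 52% to 34% (ratio 1.5), from 81% to 58% (1.8) and from 90% to 69% (2.0). The observed control median falls from about 10 to about 5.5 days.

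**Step 4: does a different rule help?** At a 20% share and hazard ratio 1.6:

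| Handling | Median 10 days | Median 28 days |
|---|---|---|
| Rule as written | 48% | 36% |
| Restrict to baseline 4 or less | 56% | 43% |
| Require improvement on baseline | about 63% | 50% |

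The last row assumes that treatment acts equally on the event required of patients starting at 5.

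**The case against.** **Few patients may be affected.** Radiographic pneumonia is mandatory, the rationale concerns hypoxemia, and the synopsis names reduced oxygen requirement among its key secondary endpoints. Most patients may start at 4. This stands: the share could be close to zero. But none of these passages excludes a patient who is not on oxygen.

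**Heart rate.** A reader might infer that heart rate above 125 is a settled route to the same result. The documents do not support that. Criterion 4 names it, but the appendix it cites omits it, and the synopsis speaks of WHO-defined severe disease. The point rests on respiratory rate, which both texts list.

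**Timing.** A reader might also infer events at time zero. Time runs from randomization, which is scheduled for Days -2 to 0. The event falls on Day 1, and only if the patient is still off oxygen then.

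**Not all the loss comes from the rule.** Patients already at 5 cannot show recovery from oxygen need under any rule. At a 20% share and a 10-day median, power falls by 63 − 48 = 15 points. Leaving those patients out still loses 63 − 56 = 7 points, so counting them on Day 1 costs the other 8. This stands, and it is why the comparison in Step 4 matters.

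**Named endpoint.** The plan adopts an established recovery definition, and a mixed threshold departs from it. This is a real cost, taken up in the fix.

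**Conclusion.** The gap is real and follows from the plan's own text: the recovery rule, applied as written, can score an untreated, severely ill patient as recovered on Day 1. The direction of the effect is certain: noise is added and the difference between arms is diluted. Its size is not known. Under the stated assumptions, power falls by about 5 to 9 points at a 10% share (63 to 58; 49 to 40) and by about 20 points at 30% (63 to 42; 49 to 29). These levels depend on the assumed control median and hazard ratio, neither of which the plan gives.

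A reader might infer that the trial's main result is at risk. It is not. The primary endpoint of ventilation or death, its sample size, the interim analysis and the safety rules do not use this scale. The matter is a minor but worthwhile correction to one secondary endpoint for which no power is claimed.

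**What to change.** Derive each patient's baseline NIAID score before the first dose and add it to the baseline characteristics in Section 15.1, which now list neither the score nor oxygen use. Define recovery as the first day with a score of at least 5 that is also higher than baseline, so at least 6 for a patient starting at 5. State how a patient who starts at 5, worsens and returns to 5 is counted. Add a sensitivity analysis restricted to baseline scores of 4 or less, or make that the main analysis and the improvement rule the sensitivity. Fix the choice before unblinding; any handling chosen afterwards would be post hoc.

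The cost is endpoint wording and one derived field. The scale is defined for each study day, and Section 5.6 already records daily maximum oxygen. The downside of the improvement rule is a small departure from the single named threshold, with two kinds of event in one test: coming off oxygen, and no longer needing medical care. The downside of the restriction is a slightly smaller analysis set.

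Separately, criterion 4 and Appendix A must be reconciled. Besides heart rate, they differ on respiratory rate (at least 30 against above 30) and saturation (below 93% against 93% or below), and severe respiratory distress appears only in the appendix.

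### The 40% and 15% planning rates are not shown to cover the high-flow and Bi-PAP events that the primary endpoint counts, and the planned Fisher test has 75.5% power at those rates, not >80%

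*Combined protocol and SAP*

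**What the plan says.** All of the following are in section 15.1 unless stated.

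- **Event.** The primary efficacy definition lists intubation, high-flow O2, Bi-PAP and AIRVO as examples of mechanical ventilation. The proportion free of these ("Bi-PAP or AIRVO) and who survive to 4 weeks after randomization will be used as the primary measure of efficacy") is the endpoint. The same parenthesis recurs in sections 5.6, 8.1, 9.2 (exclusion 1) and 12.
- **Control rate.** "The reported incidence of death or mechanical intubation for patients with severe COVID-19 is approximately 40" percent, citing reference 1. Local support is an ICU figure of 29% and the statement that "22% of all admitted patients are intubated, and 37% of intubated patients die in hospital".
- **Target.** The aim is to "reduce the composite incidence of death/mechanical ventilation from 40% to 15" percent. Power is then stated by "comparing a predicted proportion of 40% death or intubation in the control arm to 15% death or intubation in the experimental arm".
- **Test.** For sizing, "The calculation is based on 10% type 1 error rate and two-sided Mantel-Haenszel test", with 40 per arm and one interim look at half the sample. For the analysis, Fisher's "Exact test will be used to test the difference between the two arms".
- **Reuse of the 40%.** The Stopping Rule for Safety and Appendix H assume 40% on placebo for death or mechanical ventilation.
- **Ordinal scale.** "3) Hospitalized, on non-invasive ventilation or high flow oxygen devices" is a category of its own, apart from invasive ventilation/ECMO (2) and death (1).

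**The concern.** One pair of rates serves two events that the trial's own ordinal scale keeps apart. A patient who moves to high-flow oxygen and is never intubated has a primary event under the definition, but not under the wording that supports the 40%.

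Two things are at stake. First, the power claim is not tied to the event that will be tested. Counting high-flow and non-invasive support can raise the event rate. Excluding patients already on such support (section 9.2) may lower it compared with the severe patients behind the 40%. The drug's effect on the added events is also unknown. Second, interpretation suffers: death and ICU transfer are secondary endpoints, but no named endpoint isolates death or invasive ventilation. A result driven mainly by high-flow use would be only partly visible.

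A related gap lies in the same paragraphs: power was computed for one test and the analysis names another.

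**Working it through.** **1. What supports the rates.** The power paragraph speaks of intubation. Section 3.3 describes reference 1 only as one third ventilated and one third dead among severe patients, without saying what counted as ventilation. From those two fractions the composite lies between 33% (complete overlap) and 67% (none), so 40% is compatible but its coverage is not stated. The local figures include no high-flow or non-invasive rate.

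**2. Reproducing >80%.** Inputs: n = 40 per arm, p1 = 0.40, p2 = 0.15, two-sided alpha 0.10.

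- Normal approximation: pooled p = (0.40 + 0.15)/2 = 0.275; s0 = √(2 × 0.275 × 0.725/40) = 0.0998; s1 = √((0.40 × 0.60 + 0.15 × 0.85)/40) = 0.0959. Power = Φ((0.25 − 1.645 × 0.0998)/0.0959) = **81.5%**.
- Mantel-Haenszel, summing binomial probabilities over all 41 × 41 outcome tables. With a events in one arm, m in total and N = 80: Z = (a − nm/N)/√(n²m(N − m)/(N²(N − 1))), reject if |Z| ≥ 1.645. Power = **82.2%**.
- The interim boundary of 2.373 matches a two-look O'Brien-Fleming design at two-sided 0.10. Its final critical value is 2.373/√2 = 1.678. With that value at the final test, power = **80.8%**.

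The stated figure is therefore arithmetically sound for Mantel-Haenszel at 40/15.

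**3. The planned test.** Same enumeration, rejecting when the two-sided Fisher p ≤ 0.10: **75.5%** at 40/15. For 80% power at a 40% control rate, the difference needed is 24.5 points with Mantel-Haenszel and 26.5 with Fisher; the plan has 25.

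**4. Sensitivity to the event rate.** The documents give no rate for the broad event. Every row after the first is an assumption, not an estimate or a bound. The interim look is not modelled. For no effect on the added events, a fraction q of the remaining patients has an added event in both arms: control = 0.40 + 0.60q, treatment = 0.15 + 0.85q, with q = 1/6 and 1/3.

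| Case (control/treatment, %) | Mantel-Haenszel | Fisher |
|---|---|---|
| Plan: 40/15 | 82.2% | 75.5% |
| Lower rate, relative risk 0.375 kept: 30/11.25 | 68.4% | 58.9% |
| Lower rate, 25 points kept: 30/5 | 93.5% | 88.9% |
| Higher rate, relative risk kept: 50/18.75 | 91.2% | 87.1% |
| Higher rate, 25 points kept: 50/25 | 74.2% | 66.6% |
| No effect on added events, q = 1/6: 50/29.2 | 58.9% | 50.1% |
| No effect on added events, q = 1/3: 60/43.3 | 42.8% | 34.1% |

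Power moves both ways, depending on the control rate and on whether the drug prevents the added events.

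**The case against.** The sponsor can fairly say that 40% and 15% are planning assumptions for the endpoint as named. The power paragraph states them for death/mechanical ventilation too, and the safety rule and Appendix H do the same. The broad definition is used consistently in the operational sections, and choosing it is the sponsor's decision. The trial presents itself as a preliminary assessment of efficacy. The >80% reproduces, and the test mismatch is a separate matter from the definition.

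All of this stands, and it limits the point. A reader might infer that the 40% is an intubation-only rate, so that power for the defined event is wrong or below 80%. The documents do not support that: section 3.3 leaves the ventilation type in the source undefined, so the 40% is not shown to exclude non-invasive support any more than to include it. Nor does the table in the working demonstrate a shortfall, since its alternative rates are assumed. A reader might also suspect bias from a softer event, but section 4.2 provides for double-blinding and identical over-encapsulation.

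What the objection does not supply is any evidence that the rates apply to the event as defined. It also leaves the Fisher figure untouched.

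**Conclusion.** The point holds in limited form. The planning rates are not shown to match the defined primary event, and the direction of any error is unknown. The one shortfall that follows from the plan's own inputs is 75.5% power with Fisher's exact test at 40/15, against 82.2% (fixed-sample) or 80.8% (final critical value 1.678) with Mantel-Haenszel. That shortfall has nothing to do with how the event is defined. It assumes 40 per arm, two-sided 0.10 and, for Fisher, no interim adjustment. The effect of the definition itself cannot be sized from the documents. The change should be made: it is cheap, and it affects how the primary result will be read.

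**What to change.** 1. Use one definition of the primary event in the endpoint and power paragraphs of section 15.1. State both arm rates as assumptions for that event, with their basis. Label the 40% in the Stopping Rule for Safety and in Appendix H with the same definition. If the definition is narrowed, reconcile the parentheses in sections 5.6, 8.1, 9.2 and 12 with it.
2. Restate power at 40 per arm for the test that will be used: either 75.5% with Fisher at 40/15, or name Mantel-Haenszel as the primary test and keep about 81%. Add a short table of control rates below and above 40%, marked as assumptions, including a case with no drug effect on the added high-flow or non-invasive events.
3. If the broad definition stays, name death or invasive ventilation/ECMO (NIAID categories 1 and 2) within 29 days as a secondary endpoint. Two checks are needed. Section 12 lists starting ventilation, with high-flow included, as an example of early withdrawal. Section 8.1 only encourages withdrawn subjects to permit follow-up, while section 15.2 keeps consenting patients in follow-up. These must be reconciled so that outcome data continue to day 29. Also confirm that the mode of support is captured, because section 5.6 mentions only the maximum level of supplemental oxygen each day.

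The cost is some wording, a small table and one secondary endpoint, plus a data field if mode of support is not yet recorded. The stated power becomes less favourable if Fisher stays, and the sponsor would have to accept or address that. Narrowing the definition touches more sections and would leave fewer events.
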